6.2.4 Outcomes

6.2.4.1 Primary Outcomes

Primary Outcome: Infection-related Total Admitted Hospital Days

Infection-related total admitted hospital days will be calculated by two methods for the FAS population. First, LOS will be calculated by inpatient only stays and second, LOS will be calculated by inpatient stays including time spent in prolonged observation status (> 1 day). Descriptive statistics for the primary

[REDACTED]

outcome will be shown in a table by initial care, follow-up, and overall for the pre-period and post-period, and depicted graphically overall using box plots. Patient counts and percentages will be given for the primary outcome (e.g., 0 day, 1 day ... > 5 days). Descriptive statistics in the table will be repeated by all patients and patients who complete the study for comparison.

The primary analysis will consist of Hypothesis testing using a two sided (two sample equal-variance) t-test, with a significance level of 0.05, comparing the difference in total time (in days) spent in hospital between the pre- and post-periods. Violations of assumptions for the t-test in the data will be checked for. An appropriate alternative method will be selected if a major violation to an assumption is present, such as the Mann-Whitney U test². Overall differences in descriptive statistics between the pre- and post-periods for infection-related total admitted hospital days will be reported.

Because the baseline characteristics of the pre-period may differ from those of the post-period, a secondary analysis using a multivariate regression analyses, specifically a generalized linear mixed model (GLMM), [REDACTED]. As the outcome is expected to be heavily right skewed, the number of hospital days will be modeled assuming a negative binomial distribution with log link. If the model does not converge or fit, an alternate distribution will be selected. This model will assume mutual independence between the sites. Similar to above, the multivariate analysis will be completed for the primary outcome for inpatient stays only as well as including time spent under observation, as well as for all patients and patients who complete the study for comparison.

Clinically relevant baseline characteristics of interest for the adjusted analysis (as described in Section 4.1) including the following variables: age, gender (Male, Female), race (White/Caucasian, Black or African American, Other), employment status (Full-Time, Part-Time, None), insurance plan type (Private commercial plan, Government funded, Uninsured, Other), Charlson Comorbidity Index, lesion surface area (<75cm cm², =>75 cm² - 150 cm², >150 cm²), infection type (Wound infection, Cellulitis/erysipelas, Abscess), prior health resource use (Yes, No, Unknown), prior antibiotic treatment failure (Yes, No, Unknown), presence of SIRS criteria (<2 or >=2), presence of recurrent infection in prior 6 months (Yes, No, Unknown), any health resource use in prior 3 months (Yes, No, Unknown), as well as is patient was immunocompromised (Yes, No, Unknown). Patients will be defined as immunocompromised if they have evidence of any of the following at baseline: Connective tissue disease, diabetes mellitus, leukemia, or malignant lymphoma. These characteristics will be selected for the GLMM model by use of stepwise selection with the [REDACTED] procedure and a statistical significance level of <0.1. Categorical variables will be collapsed where possible. The primary predictor variable will be a pre/post-period indicator, and potentially other selected characteristics will be forced into the model based on clinical rationale and distributions observed in the data (specifically

imbalance between the pre- and post-periods); as it is assumed that patients enrolled in each site will be correlated, a generalized linear mixed model (GLMM) will be generated. The GLMM will adjust for correlated data among patients at sites by using a RANDOM statement in analyses. The Kenward and Roger method for approximating degrees of freedom will be taken for inference on the fixed effects. The final model results will be presented in a table.

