4.1 Study outcomes

4.1.1 Baseline characteristics

Baseline characteristics will be collected following subject enrollment into the study, and will be based on physical examination and medical history. A complete list of baseline characteristics is shown in Table 2.

Table 2. Baseline characteristics

Measure Type	Description
Demographics	Age (in years) Gender Race Employment status Location subject presents from (e.g. from home, LTC, SNF, nursing home)
Comorbidities	Myocardial infarction Congestive heart failure Peripheral vascular disease Cerebrovascular disease Dementia Chronic pulmonary disease Rheumatologic disease Peptic ulcer disease Mild liver disease Diabetes without complications Diabetes with complications Renal disease Moderate or severe liver disease (Child-Pugh Class B and C) Any malignancy, including leukemia and lymphoma Metastatic solid tumor If subject has cancer, whether active vs. remitted/cured Alcohol/drug abuse/illicit needle use Malnutrition HIV

Measure Type	Description
	Immunocompromising conditions other than HIV Altered mental status
Charlson Comorbidity Index ^b (CCI)	Derived variable based on recorded comorbidities: Calculation of the CCI for each subject at baseline to assess the risk of 1 year mortality
Infection type	Cellulitis/erysipelas, wound infection, or major cutaneous abscess
Infection characteristics	Lesion size (as described in Appendix A) and location Thrombocytopenia (<150,000 platelet count or site-specific definition) Hyperglycemia (>120mg/dL blood glucose or site-specific definition) Hyponatremia (<135 mEq/L blood sodium or site-specific definition) Acidosis (<7.35 pH of the blood or site-specific definition or described in medical chart) Uremia (as described in medical chart) Anemia (14-18 g/dL hemoglobin for men or 12-16 g/dL hemoglobin for women or site-specific definition) Fever (>98.6 degrees Fahrenheit or site-specific definition) SIRS criteria ^c at enrollment, including highest or lowest recorded RR and highest or lowest recorded BPM/highest or lowest recorded fever/highest or lowest WBC count or amount of immature cells Highest or lowest recorded BP at enrollment Laboratory results at baseline and during follow-up (e.g. Total white blood cell count, hemoglobin, sodium, glucose, serum creatinine, and C-reactive protein)

^b Deyo et al 1992

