5.10 Potential Hy's Law cases

Every subject that meets potential Hy's law criteria,

- ALT or AST $\geq 3 \times \text{ULN}$ AND
- Total Bilirubin $\geq 2 \times \text{ULN}$ AND
- Alkaline Phosphatase $< 2 \times \text{ULN}$

occurring anytime from the time he or she signs the ICF for the trial until the final follow up visit, investigators will notify the sponsor immediately when all the above criteria have been met. A potential Hy's law case will be sent directly to the sponsor by emailing [contact] on an AE of Special Interest Form along with the SAE Report Form as soon as possible (within 24 hours of learning of the potential Hy's law). The CRF for potential Hy's law cases will be completed within seven calendar days. Every effort to determine the cause of the liver enzyme abnormalities will be made, and close monitoring will be initiated in conjunction with the medical monitor and in accordance with the FDA "Guidance for Industry: Drug Induced Liver Injury- Pre-Marketing Clinical Evaluation" July 2009.

6 Data analysis

Frequency and proportion of subjects deemed eligible and ineligible for study enrollment based on each of the inclusion/exclusion criteria will be summarized. The frequency and proportion of subjects who successfully complete the study, withdraw, were lost-to-follow-up, and who terminated the study early, will also be reported. Subject characteristics at baseline will be summarized and described for all enrolled subjects and compared between the pre- and post-periods. Site characteristics will also be described. Descriptive statistics (count, mean, standard deviation, range for quantitative variables, and counts and percentages for categorical variables) will be reported for all outcomes. The difference in study outcomes between the pre- and post-period will be assessed using appropriate statistical methods, accounting for study site, with adequate power. The primary outcome will be tested for simple superiority, and subsequently, tested for non-inferiority with a 10% margin between the pre- and post-periods.

The primary analysis of differences in LOS is performed using a 2-sided hypothesis test of the modified intent-to-treat principle such that all evaluable patients are included in the analysis. Patients are evaluable if they received at least one dose of antimicrobial therapy for their ABSSSI. Differences in length of stay are measured by Mann-Whitney U test.

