3.0 Study Design

This study will employ a “pre-post” pragmatic design, which will consist of both a pre-period, or an observational baseline period, and a post-period, or an interventional period. The pre-period and post-period will consist of independent groups of patients. During the pre-period, the site will implement the first component of the critical pathway through implementation of guideline-based criteria to identify patients admitted to the hospital, obtain informed consent, and monitor enrolled subjects. The site will initiate treatment for ABSSSI with “usual care,” defined as site- or physician-specific antibiotic treatment of ABSSSI with coverage for a known or suspected Gram-positive infection (e.g., vancomycin, linezolid, and daptomycin) to each study patient who meets all inclusion and exclusion criteria. Blinding of treating physician to patient enrollment in the study during the pre-period will ensure unbiased provision of usual care. During the post-period, for all patients who provide informed consent and are subsequently enrolled, each participating site will additionally implement the second component of the new critical pathway, use of dalbavancin, at the point of care in the hospital or other designated site to each study patient who meets all inclusion and exclusion criteria.

For both periods of interest, patient follow-up spans the period beginning on the day of study enrollment and ends 44 days thereafter, which incorporates an initial care period of 14 days (reflecting the 10–14-day period during which most antibiotics are anticipated to be required for care of ABSSSI) and a subsequent “follow-up” period of 30 days. Study measures will be collected as described in the protocol and will be based on medical records, unless otherwise indicated.

A schedule of assessments is provided in Appendix A. Follow-up visits will be scheduled for approximately 48-72 hours after enrollment (both periods), 10-14 days after enrollment (both periods), and 44 days after enrollment (both periods). Any additional visits to the visit schedule given in Appendix A will be at the discretion of the patient and treating physician.

The duration of the study was not predetermined; it is dependent on the time required to enroll the necessary number of eligible patients (43 patients per time period; 86 patients enrolled in all).

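### The primary comparison of two non-randomised periods is unadjusted, although the SAP expects baseline differences and collects the data to adjust for them

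*SAP*

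**What the plan says.** SAP 3.0 describes the two groups: "The pre-period and post-period will consist of independent groups of patients". They come from consecutive calendar periods and are not randomised. SAP 2.1 sets the primary objective as estimating a difference in infection-related hospital days.

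The deciding test is in SAP 6.2.4.1: "The primary analysis will consist of Hypothesis testing using a two sided (two sample equal-variance) t-test, with a significance level of 0.05". The Mann-Whitney U test is the fallback if the t-test assumptions fail badly. Protocol section 6 (Data analysis) names the rank test instead: "Differences in length of stay are measured by Mann-Whitney U test". Neither test uses covariates.

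The SAP then gives its reason for a further model: "Because the baseline characteristics of the pre-period may differ from those of the post-period, a secondary analysis using a multivariate regression analyses". This is a negative binomial mixed model with a log link. Its candidate list is introduced as "Clinically relevant baseline characteristics of interest for the adjusted analysis" and includes age, Charlson index, infection type, lesion area and SIRS status. On how they enter the model: "These characteristics will be selected for the GLMM model by use of stepwise selection", at a significance level below 0.1. Other variables may be forced in on clinical grounds and according to the imbalance seen in the data.

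The values needed are collected. Protocol 4.1.1 says: "Baseline characteristics will be collected following subject enrollment into the study, and will be based on physical examination and medical history".

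**The concern.** The t-test compares the periods as if they differed only by the pathway and by chance, and nothing in the design secures that for patient-level case mix. Protocol 3.1.2 claims only that the design removes site-level confounding. Two features could shift case mix between periods:

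- **Enrolment.** In the pre-period the coordinator or core-team physicians decide, and the treating physician is blinded to that decision (Protocol 3.3.1). In the post-period the treating physician may apply the checklist and enrol (Protocol 3.3.2).
- **Analysis set.** Any antibiotic dose qualifies a pre-period patient, but only dalbavancin qualifies a post-period patient (SAP 6.1.1).

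If post-period patients have milder or less complicated infections, their shorter stay is counted as a pathway effect. If they are sicker, a real benefit is hidden. The SAP names this risk, yet rests its conclusion on the analysis that does not address it. It also gives no rule for the case where the adjusted and unadjusted results disagree.

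**Working it through.** **Inputs from the documents** (Protocol 6.3, SAP 6.1.2): SD 3.0 days, difference 2 days, two-sided 0.05, 80% power, 37 per period, raised to 43 for attrition.

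**Assumed inputs**, because the documents give none: correlation r between a baseline covariate and stay of 0.3 to 0.5, and imbalance d between periods of 0.3 to 0.5 SD.

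**1. The plan's own figure.** The normal approximation is n = 2 × 3.0² × (1.960 + 0.842)² / 2² = 35.3, so 36. The exact noncentral t gives 79.7% power at 36, 80.8% at 37 and 86.3% at 43. The stated 37 is reproduced.

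**2. Precision of the unadjusted difference at 43 per period.** SE = 3.0 × √(2/43) = 0.647 day. The smallest significant difference is 1.989 × 0.647 = 1.29 days.

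**3. Bias and false positives if the pathway has no effect.** Bias = r × d × 3.0. The rejection rate is from the noncentral t with 84 degrees of freedom.

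| r | d (SD) | Bias (days) | Two-sided type I error |
|---|---|---|---|
| 0.3 | 0.3 | 0.27 | 7.0% |
| 0.3 | 0.5 | 0.45 | 10.6% |
| 0.5 | 0.3 | 0.45 | 10.6% |
| 0.5 | 0.5 | 0.75 | 20.9% |

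Against the planned 2-day effect, the bias is 0.27/2 = 14% to 0.75/2 = 38%. Its sign is not known.

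**4. After adjusting for that one covariate.** In 20,000 simulated trials per scenario (linear model, normal data), bias was about 0 and type I error 4.9–5.1%. Power for a true 2-day difference was 87–93% at 43 per period and 82–89% at 37.

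**5. Does the interval narrow?** With one covariate the SE is multiplied by √[(1 − r²)(1 + d²/4)].

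| r | d = 0 | d = 0.3 | d = 0.5 |
|---|---|---|---|
| 0.3 | 0.954 | 0.965 | 0.983 |
| 0.5 | 0.866 | 0.876 | 0.893 |

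The gain is 5–13% with a balanced covariate and about 2–12% with imbalance. With seven covariate terms and all the prognostic value in one of them (simulated, 43 per period, imbalance 0.3–0.5 SD), the SE is 7–9% smaller at r = 0.5 but 1–3% larger at r = 0.3. In that last case, at 3% larger, 2/(0.647 × 1.03) = 3.00 and 3.00 − 1.99 = 1.01, so power is about 84%. With 37 per period the same arithmetic gives 2/(0.697 × 1.03) = 2.79 and about 78%.

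**6. Degrees of freedom.** Age 1, Charlson index 1, infection type (three levels) 2, lesion area (three categories in the SAP) 2, SIRS met 1: a total of 7, or 6 if lesion area is continuous.

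**7. Scale.** The log link gives a ratio of mean days. The objective in SAP 2.1 is a difference in days, so the planned adjusted model does not report the primary quantity directly.

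**The case against.** The SAP does not ignore confounding. It plans an adjusted model of the same outcome, for both definitions of stay and for all patients and completers, from a named candidate list. It also compares baseline characteristics between periods (SAP 6.2, 6.2.3). Both periods share one site, the same eligibility criteria and the same checklist, which restricts case mix. Parts of the model description are redacted, so its full specification cannot be judged. The sizes above rest on assumed values, and 21% is the extreme corner. A negative binomial model is also a reasonable choice for an outcome the SAP expects to be heavily right-skewed.

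All of this stands, and it limits the point to the ranking and specification of analyses already planned. Three stronger readings are tempting but not supported:

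- **That the primary comparison has no protection against case-mix differences.** The shared site, criteria and checklist give some, and the secondary model gives a further check.
- **That the trial's false-positive rate is 21%, or that bias favours the pathway.** The documents give no correlation, no imbalance and no direction.
- **That adjustment will also tighten the interval.** At r = 0.3 with seven terms it does not.

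The objection does not remove the central problem. The result that decides the trial is the unadjusted one, and the adjusted result is not fixed in advance.

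**Conclusion.** The point holds as a matter of which analysis is primary. The unadjusted t-test carries any case-mix difference straight into the estimate, and the planned adjustment is secondary, data-driven in its covariates and on a different scale from the objective. Under the assumed correlation of 0.3–0.5 and imbalance of 0.3–0.5 SD, with the plan's SD and 43 per period, the bias is 0.27–0.75 day in either direction and two-sided type I error is about 7–21%. These figures come from a linear model with one normal covariate, so for skewed day counts they are illustrative.

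A reader might infer that adjustment would make the two periods comparable as randomised groups are. It would not: it leaves calendar trends and unmeasured selection untouched. The gain is less bias from measured factors, and the change is a cheap improvement.

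**What to change.** In SAP 6.2.4.1, before database lock:

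- Make the primary estimate the adjusted pre/post difference in mean days, with its 95% interval, from a regression with a fixed list: age, Charlson index, infection type, lesion area and SIRS met. Use robust standard errors, name the variant, and allow no stepwise selection or data-dependent forcing.
- State a rule that keeps patients with a missing covariate in the analysis, for example multiple imputation of the baseline value. SAP 6.1.5 otherwise imputes nothing outside validated instruments and Protocol 6.2 expects missing data, so a patient without a lesion measurement would drop out of the adjusted model but not out of the t-test.
- Report the unadjusted t-test beside it, and keep the negative binomial model as supportive.
- Record the change in SAP 5.0, which already explains the move away from the protocol's Mann-Whitney test.
- State in the report that calendar trends and unmeasured selection remain.

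**Cost:** SAP wording, 6–7 degrees of freedom out of 86 patients, a modelling assumption and the missing-covariate rule. No new data are needed. At 43 per period power for the 2-day effect stays above 80% in the scenarios shown. In the least favourable one, with only 37 analysed per period, it is about 78%.

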1.1.2 Acute bacterial skin and skin structure infections

In an effort to focus on acute infection and increase homogeneity of what had traditionally been a relatively diverse population, in 2013 the US Food and Drug Administration (FDA) provided guidance to manufacturers developing antibiotics for a subgroup of SSSI known as acute bacterial SSSI (ABSSSI). The FDA defined ABSSSI to consist of cellulitis/erysipelas, wound infection, and major cutaneous abscess. To be deemed ABSSSI, the infection should have a lesion surface area ≥75 squared centimeters (cm²); additional criteria set forth by the FDA¹ were infection-specific and included:

- Spreading areas of redness, edema, and/or induration (cellulitis/erysipelas)
- Purulent drainage from a wound with surrounding redness, edema, and/or induration (wound infection)
- Pus within the dermis or deeper that is accompanied by redness, edema, and/or induration (major cutaneous abscess)

ABSSSI are often caused by Gram-positive pathogens, including but not limited to *Staphylococcus aureus* (both methicillin-resistant [MRSA] and methicillin-susceptible strains [MSSA]) and *Streptococcus pyogenes*.¹

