3.4.1 Inclusion criteria

Eligible study subjects satisfy all of the following inclusion criteria^{1,10,24}

- Aged ≥ 18 years
- Admitted patients who meet clinical definition for ABSSSI¹⁰⁻¹¹
 - Present with the following infection types: cellulitis/erysipelas, wound infection, or major cutaneous abscess
- Known or suspected infection caused by susceptible isolates of the following Gram-positive microorganisms: *Staphylococcus aureus* (including methicillin-susceptible and methicillin-resistant strains), *Streptococcus pyogenes*, *Streptococcus agalactiae*, *Streptococcus dysgalactiae*, *Streptococcus anginosus group* (including *S. anginosus*, *S. intermedius*, *S. constellatus*) and *Enterococcus faecalis* (vancomycin susceptible strains).
- Willing and able to return to the hospital or a designated clinic for scheduled visits, or be in contact with the study coordinator through telephone communication, as required by the protocol and the antibiotic treatment administered

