reason, admission to the ICU and primary reason, ED visits or other outpatient visits (e.g., infusion center and physician’s office) and primary reason, use of dialysis, use of any medications for chronic diseases and specifically use of an antibiotic medication, prior antibiotic treatment failure (determined by discontinuation of treatment due to worsening or recurrent ABSSSI or the occurrence of an adverse event related to the antibiotic), and receipt of wound care for the presenting infection.

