6.1 General Considerations

6.1.1 Analysis populations

Enrolled Set

The enrolled set consists of all patients who have signed informed consent and met all study eligibility criteria. Data will be summarized on disposition and baseline characteristics. Output will be summarized by study period (pre-period vs. post-period). All data listings will be reported for the enrolled set unless specified in Section 5.2.

Full Analysis Set

The full analysis set (FAS) population consists of all enrolled patients. Additionally, patients in the pre-period must receive at least one dose of antibiotics and patients in the post-period must receive at least one dose of dalbavancin for inclusion. All patients in the pre-period and post-period will be analysed. Data will be summarized by study period.

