6.2.3 Infection Characteristics at Baseline and Follow-up

Infection characteristics at baseline and the day 10-14 follow-up visit will be reported in tables for the FAS population. As applicable, patient counts and percentages will be summarized for primary infection type, purulent drainage from primary lesion, any pain with primary lesion, tenderness of primary lesion, primary lesion location, primary lesion size ($75\text{cm}^2 - 150\text{cm}^2$, $\geq 150\text{cm}^2$) number of additional lesions (e.g., 0, 1, 2, ≥ 3), fever, SIRS (met i.e., ≥ 2 criteria present, by individual criteria, and by number of criteria met), and recurrent/ABSSSI infection in prior 6 months. Descriptive statistics will be summarized for primary lesion size and pain on a 10-point scale. Differences in infection characteristics between the pre- and post-period will be assessed using statistical significance testing. All of the aforementioned variables will be reflected in listings.

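### In the secondary adjusted analysis of hospital days, lesion area is expected to reduce to a single cut at 150 cm² and prior healthcare use is listed twice as a yes/no/unknown flag, although finer data are already collected

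*SAP*

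**What the plan says.** SAP 6.2.4.1 adds a negative binomial mixed model as a secondary analysis of the primary outcome, because patients in the two periods may differ at baseline. Its covariates are candidates for stepwise selection at p < 0.1. Some may be forced in for clinical reasons or because of imbalance, and categories may be collapsed.

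Lesion size enters the candidate list as "lesion surface area (<75cm cm², =>75 cm² - 150 cm², >150 cm²". Elsewhere:
- Protocol 1.1.2 gives the ABSSSI definition: "the infection should have a lesion surface area ≥75 squared centimeters".
- Protocol 3.4.1 requires "Admitted patients who meet clinical definition for ABSSSI". The visible criterion states no area.
- SAP 6.1.1 limits the enrolled set, from which the full analysis set is drawn, to "all patients who have signed informed consent and met all study eligibility criteria".
- SAP 6.2.3 tabulates lesion size in classes that start at 75 cm², and also as a measurement: "Descriptive statistics will be summarized for primary lesion size and pain on a 10-point scale".
- Protocol appendix 11.1 obtains area as length times perpendicular width.

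Prior use appears twice in the same list. One entry has no time window. The other is "any health resource use in prior 3 months (Yes, No, Unknown". SAP 4.1 and Protocol Table 2 collect use for the prior three months only, over items from hospitalization and ICU admission to "use of dialysis, use of any medications for chronic diseases and specifically use of an antibiotic medication". SAP 6.2.2 tabulates hospitalizations, ICU admissions, surgery and ED or outpatient visits separately.

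**The concern.** The periods are not randomized, and this is the only baseline-adjusted analysis of the primary outcome that the SAP describes. Lesion size and recent hospitalization could plausibly affect days in hospital. If either differs between periods and enters the model in coarse form, part of the difference stays in the estimated period effect, even though the results table lists the variable among the adjusters. Both are recorded in more detail than the model would use.

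**Working it through.** **Design figure.** The planned difference is 2 days, the SD 3, two-sided alpha 0.05 and power 80%. The normal approximation gives 2 × (1.96 + 0.842)² × (3/2)² = 35.3, so 36 per period. The t-test calculation gives 36.3, so 37, as stated in Protocol 6.3 (power 0.808). Nothing below changes this.

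**Is the lowest class populated?** The definition is at least 75 cm², patients must meet the definition, the analysis set requires eligibility, and the descriptive classes begin at 75. The class below 75 is therefore expected to be empty. The model is left with two classes, split at 150 cm².

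**What the split leaves behind (large samples).** The documents give no areas, so these inputs are assumptions: log-normal area truncated at 75 cm², median before truncation 120 to 300 cm², log-SD 0.5 to 1.0, post-period median 25% lower, outcome linear in log area. Share of confounding removed by the split:

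| Median before truncation (cm²) | log-SD 0.5 | log-SD 0.8 | log-SD 1.0 |
|---|---|---|---|
| 120 | 67% | 64% | 59% |
| 200 | 60% | 55% | 50% |
| 300 | 37% | 43% | 42% |

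So 33% to 63% remains. More remains as lesions get larger, because fewer patients fall below 150.

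**At the trial's size.** Simulation assumptions: 43 per period, negative binomial with mean 4 and SD 3, 42% longer stay per SD of log area, 0.3 SD imbalance, medians 200, 300 and 450 before truncation. Bias in the log ratio with the covariate always in the model:
- none: −0.088, −0.089, −0.089
- split at 150: −0.053, −0.054, −0.064 (60%, 61% and 72% of the unadjusted bias)
- continuous log area: −0.015, 0.001, 0.006

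A further simulation that includes the p < 0.1 step gave about −0.10 to −0.12 unadjusted, −0.06 to −0.07 with the split, and within about 0.02 of zero with continuous area. The continuous term was retained about 99% of the time, the split 85% to 91%.

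**Scale of that bias.** The planned fall from 4 to 2 days is a log ratio of ln(0.5) = −0.693. With the same coefficient of variation in both periods, the standard error is about √(2 × (3/4)² / 43) = 0.162. A residual bias of 0.05 to 0.07 is 7% to 10% of the planned effect and 0.31 to 0.43 of a standard error.

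**Prior use.** Suppose 15% were hospitalized in one period and 30% in the other, with 1.5-fold stay if hospitalized. The confounding ratio is (1 + 0.5 × 0.30)/(1 + 0.5 × 0.15) = 1.07. If the flag is Yes for a share s, and all hospitalized patients are Yes, the ratio within Yes is (1 + 0.5 × 0.30/s)/(1 + 0.5 × 0.15/s): 1.073, 1.077 and 1.086 for s = 0.95, 0.90 and 0.80. In that range the flag removes nothing. A different assumption gives a different answer: with use as a count of mean 0.5 to 3, 30% lower in the post-period and acting linearly, the flag removes 21% to 80%. A second copy of the same flag adds nothing.

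**Degrees of freedom.** In the SAP's order (age, gender, race, employment, insurance, CCI, lesion area, infection type, prior use, antibiotic failure, SIRS, recurrence, three-month use, immunocompromised): 1 + 1 + 2 + 2 + 3 + 1 + 2 + 2 + 2 + 2 + 1 + 2 + 2 + 2 = 25 for 86 patients. One continuous lesion term saves 1. One yes/no use term in place of two three-level flags saves 3. That leaves 21.

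**The case against.** Several points on the other side stand.

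- The empty class is inferred. The 75 cm² figure is in the protocol's background, parts of the exclusion list are redacted, and the classes in SAP 6.2.3 also serve day 10–14, when lesions may have shrunk below 75, so they are weak corroboration. An empty class causes no bias, and collapsing would remove it.
- The covariates are candidates, not fixed terms. With 86 patients and p < 0.1, a one-degree-of-freedom covariate with partial correlation 0.10, 0.20 or 0.30 is retained with probability about 0.24, 0.58 or 0.88. Omission may matter more than coding. The coding point survives, because the continuous term did better with selection included, and forcing in the split would still adjust only partly.
- Duplicate flags do no harm by themselves; if they are identical, selection keeps at most one. Prior antibiotic failure is a separate candidate, so prior use is not reduced wholly to one flag. SIRS, infection type and CCI, also candidates, could absorb some lesion-size confounding.
- The residual bias is modest: at 0.05 to 0.06, coverage of a 95% interval falls only to about 94%.

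A reader might infer that most of a lesion-size imbalance, and essentially all of an imbalance in hospitalization, is left unadjusted. The documents do not support that. Both depend on distributions they do not give. The second also needs nearly every patient to be Yes, and the SAP does not define which services the flag counts.

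**Conclusion.** The point holds as an inefficiency in a secondary model. The lesion covariate is expected to reduce to one cut at 150 cm². Under log-normal areas with medians of 120 to 300 cm² before truncation, the cut leaves roughly one third to two thirds of any lesion-size confounding; the simulation with the largest lesions left slightly more, 72%. Continuous log area removes nearly all of it if the relation is linear on that scale, and is more likely to be selected. The two use entries appear to be the same variable, although their wording differs. How poorly the flag captures recent hospitalization cannot be settled from the documents. The primary t-test and the sample size are untouched. Label: cheap improvement.

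**What to change.** In the SAP 6.2.4.1 covariate list:
- Replace the three lesion classes by log of baseline primary lesion area, as one continuous term. Keep size classes for descriptive tables only.
- Delete one of the two prior-use entries, and define the other explicitly from data that SAP 6.2.2 already tabulates, for example hospitalized in the prior 3 months (Yes/No). A count is a reasonable alternative. A hospitalization flag sets aside ED, ICU, surgical and outpatient use, so the choice should be stated with its reason.

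The cost is SAP wording. No new data are needed, and the candidate list falls from 25 to 21 degrees of freedom with the example coding. The downside is an assumption of linearity in log area, which a residual plot can check. Recoding does not guarantee that either variable is selected; if adjustment for them is wanted regardless, the SAP's existing provision for forcing terms in should name them.
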